## **8. SUBJECT SAFETY MONITORING**

Patients will be monitored by CES Staff, including PI, nurse practitioner and fellows, and by [name], a board-certified pediatric neurologist, who is a

special volunteer with clinical privileges at NIH, and has the world's largest experience with SSADH deficiency.

[name] will serve as Independent Study Safety Monitor (ISSM). [name] is a Board-Certified Neurologist with Fellowship training in Movement Disorders who is conducting clinical research with [name].

The ISSM will serve as the IND sponsor's medical monitor and will make the final determinations of relatedness of safety events to the investigational product on behalf of the sponsor (NINDS). The ISSM will review serious adverse events, and serious unanticipated problems. SAEs that are at least temporally associated with the use of the study drug (whether assumed to be related or not) will be given to the ISSM immediately, but no later than 48hrs from the time the PI learns of an event. The PI will record nonserious AEs and report them to the ISSM at the time of 1) IRB continuing review and 2) the annual Safety Monitoring Committee's annual meeting. The ISSM will review these reports and provide feedback to the PI and NINDS in a timely manner.

Patients will be monitored carefully by CES clinicians for any change in their clinical status during clinic visits and self-report during phone and computer contact. Intervention will be determined by the independent subject safety monitor and may include consultation, additional studies, or withdrawing the patient from the protocol.

Parameters to be monitored include seizure frequency, neurological examination, fluctuations in cognitive and behavioral features. Specific drug-related side effects to be monitored include headache, tiredness, nausea and vomiting, sleepiness and dizziness.

Patients who cannot tolerate the study drug will be taken off of it. Following review and approval by the Independent Subject Safety Monitor, patients who stopped taking the study drug can remain in the study and complete follow-up visits and assessments.

Females who become pregnant will stop the study drug however will remain in the study and can be followed under the protocol. They will not complete any assessments that pose risk to the pregnancy or fetus but can do other non-invasive procedures such as neuropsychological testing. They will be followed until the end of the study or pregnancy outcome, whichever is later.

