Patients will be removed from the study if they are unable to cooperate, or have an alteration in clinical status needing medical intervention. Patients may withdraw from the trial at any time at their own request. The Investigators may withdraw a subject for safety or behavioral reasons.

Toxicity will be graded according to the NCI Common Terminology Criteria for Adverse Events (appendix 2). Dose limiting toxicities will be considered any NCI grade 3 toxicity felt to be probably or definitely related to study medication; grade 4 or 5 toxicity judged to be possibly, probably or definitely related to study medication by the safety monitor.

In the event of a Grade 3 toxicity felt to be probably or definitely related to study medication by the study investigator or safety monitor, one-step dose reductions will be initiated until the toxicity resolves. If NCI Common Terminology Grade 4 toxicity is felt to be possibly, probably or definitely related to study medication by the study investigator, the patient will be withdrawn from the study medication. All dose changes and/or dose interruptions will be recorded on case report forms.

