### **8.1 Criteria for Breaking the Blind and Premature Termination or withdrawal**

Criteria to be used to decide whether a report or test result requires intervention include Grade 3 NCI CTC toxicity, a laboratory test twice the upper limit of normal, an abnormal finding on EEG or ECG not present at baseline. Intervention will be determined by the safety monitor and may include consultation, additional studies, or withdrawing the patient from the protocol.

The blind for an individual may need to be broken even for non-serious, expected, or unrelated AEs or as requested by local regulatory authorities or where, in the view of the safety monitor, knowledge of the identity of the study drug is essential to appropriately manage an adverse event.

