Seizures are a clinical feature of SSADH and an expected event for this population. This patient population may experience seizures and resulting emergency room visits and/or hospitalization. We will record these events including the resulting emergency room visits and/or hospitalization as part of the adverse events reported at the time of continuing review. Reporting of seizures

and emergency-related treatment at the time of the CR is limited to emergency related seizure treatment only and all other SAEs will be reported immediately.

The ISSM will serve as the IND sponsor's medical monitor and will make final determination of relatedness of safety events to the investigational product on behalf of the sponsor (NINDS). The PI will immediately (no later than 48hrs) report SAEs that are at least temporally associated with the use of the study drug to the ISSM according to the requirements of 21 CFR 312.64(b) and as agreed upon with the sponsor. The PI will record nonserious AEs and report them to the ISSM at the time of 1) IRB continuing review and 2) the annual Safety Monitoring Committee's annual meeting. The PI will send the AE log to the IRB with the next continuing review.

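### The automatic Grade 4 drug stop acts only on the study investigator's attribution and should also act on the safety monitor's

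*Combined protocol and SAP*

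**What the plan says.** Section 8 (Subject Safety Monitoring) names the attributing role differently in three neighbouring statements:

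- **Dose-limiting toxicity, Grade 4 or 5:** "grade 4 or 5 toxicity judged to be possibly, probably or definitely related to study medication by the safety monitor".
- **Grade 3 dose reduction:** one-step reductions follow a "Grade 3 toxicity felt to be probably or definitely related to study medication by the study investigator or safety monitor".
- **Grade 4 drug stop:** if "Grade 4 toxicity is felt to be possibly, probably or definitely related to study medication by the study investigator, the patient will be withdrawn" from study medication.

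On who decides relatedness, Section 8 says that the independent safety monitor "will make the final determinations of relatedness of safety events to the investigational product" for the sponsor. Section 17 repeats that this monitor "will make final determination of relatedness of safety events to the investigational product". Section 17 also has the principal investigator, consulting the CD, determine whether serious adverse events are related to the research.

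Other text gives overlapping protection. Section 8 states: "Intervention will be determined by the independent subject safety monitor and may include consultation, additional studies, or withdrawing the patient from the protocol". Section 8.1 has a similar sentence and lists Grade 3 toxicity among its criteria for intervention. Section 8 also requires that patients who do not tolerate the drug stop it, and that patients whose clinical condition changes so as to need medical care leave the study. Neither of these two rules refers to attribution.

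**The concern.** The three statements do not fit together. For the milder grade either role can set off the mandatory action, while for the more severe grade only the investigator can. The definition of a Grade 4 dose-limiting toxicity uses the monitor's judgement, which the Grade 4 stop ignores.

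The gap is confined to one kind of disagreement: the monitor considers a Grade 4 event at least possibly related and the investigator considers it unrelated. The event is then dose-limiting by the protocol's own definition, and related in the view of the role with the final determination, yet the one automatic Grade 4 rule does not act. Stopping the drug then rests on the monitor's discretion or on the general rules.

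Such a disagreement is plausible here. Section 17 treats seizures as an expected feature of the disease, and Section 7.1 reports seizures in animals at high doses of the drug. An investigator could attribute a severe seizure to the disease while the monitor cannot exclude the drug. Section 1.4 notes that the drug has not been used in children, and Section 3.2 allows enrolment from age 4.

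**Working it through.** The plan gives no figure to reproduce. The check is a comparison of the rules, followed by a count of attribution combinations.

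**Step 1: the rules side by side**

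| Rule | Whose attribution counts | Lowest causality level | Result |
|---|---|---|---|
| Grade 3 (Section 8) | Investigator or monitor | Probably | Mandatory step-down |
| Grade 4 (Section 8) | Investigator only | Possibly | Mandatory drug stop |
| Grade 4 or 5 dose-limiting definition (Section 8) | Monitor | Possibly | Label |
| Monitor's intervention (Sections 8 and 8.1) | Monitor | None stated | Discretionary |

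The Grade 4 stop is narrower than the Grade 3 rule on who may attribute and wider on causality, so it is not narrower overall.

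**Step 2: the count.** Assume that each role chooses among four levels: not related, possibly, probably, definitely. The last three are in Section 8. *Not related* is added here to complete the scale. There are 4 × 4 = 16 pairs, written investigator/monitor.

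- Grade 3 rule, either role at least probably: 16 − (2 × 2) = 12.
- Grade 4 rule as written, investigator at least possibly: 3 × 4 = 12.
- Grade 4 dose-limiting definition, monitor at least possibly: 4 × 3 = 12.
- Dose-limiting and automatically stopped: 3 × 3 = 9.
- Dose-limiting but not automatically stopped: 12 − 9 = 3. These are not/possibly, not/probably and not/definitely.

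**Step 3: the same attributions under the two grade rules**

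- The Grade 3 rule fires and the Grade 4 rule does not in 2 pairs: not/probably and not/definitely.
- The reverse holds in 2 pairs: possibly/not and possibly/possibly.
- This is why both totals are 12.

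**Step 4: two ways to amend the Grade 4 rule**

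- *Either role suffices (at least possibly):* it fires in 16 − 1 = 15 pairs, covers 12 of 12 dose-limiting pairs and loses none that fire today.
- *The monitor's determination governs:* it fires in 12 pairs but loses 3 that are mandatory today: possibly/not, probably/not and definitely/not.

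**The case against.** The strongest case on the other side is that the gap nearly closes itself. In the disputed situation the monitor already believes that the drug may be responsible and, under Sections 8 and 8.1, already decides the intervention. Harm would require the monitor to hold that view and not act, so what is missing is compulsion and not authority. The rules on intolerance and on needing medical care are mandatory and do not depend on attribution. No other rule in the supplied text uses the dose-limiting label. The monitor's final determination is made for the sponsor, and no text says that it controls an individual patient's dosing. The 16-pair count gives every pair equal weight and says nothing about frequency. A deliberate split is also conceivable, with the investigator holding an immediate stop at a low causality threshold and the monitor holding discretion, although the documents do not say so.

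Most of this stands as a limit on the consequence. It does not make the rules consistent. The monitor's options include consultation or further tests and are not an automatic drug stop. The intolerance rule names no grade or decision-maker. The medical-care rule takes the patient out of the study, whereas the Grade 4 rule stops only the drug and Section 8 allows follow-up to continue after that. If the split was deliberate, the amendment keeps its benefit, because the investigator can still stop the drug alone.

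**Conclusion.** The concern holds. As written, a Grade 4 event that only the safety monitor considers related does not trigger the automatic stop, and no other text extends the stop to the monitor's view.

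On the assumed four-level scale the rule misses 3 of the 12 pairs that meet the Grade 4 dose-limiting definition. In 2 of those 3 the same attributions would give a Grade 3 event its mandatory step-down. How often this would arise among the 22 planned patients cannot be derived from the documents.

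The overlapping protections make this a low-cost correction to a stated safety rule. It is not evidence that patients would be left on drug, and it does not affect the sample size or the efficacy analysis. Confidence in the textual mismatch is high.

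**What to change.** In the Grade 4 sentence of Section 8, add *or safety monitor* after the reference to the study investigator. Attribution by either role at the possible level or above then stops the study medication, and neither role can cancel the other's. This matches the wording already used for Grade 3. Do not add that the monitor's determination governs dosing, since a monitor's finding of no relation could then undo an investigator-triggered stop.

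The cost is three words, with no added staff or procedures, and possibly a few more withdrawals from drug. One limit remains. The 48-hour route to the monitor in Sections 8 and 17 covers only serious events temporally associated with the drug. Grade 4 events not classed as serious are, on the stated route, reported to the monitor only at continuing review or the annual committee meeting, so the added trigger would act later for those.

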### **8.1 Criteria for Breaking the Blind and Premature Termination or withdrawal**

Criteria to be used to decide whether a report or test result requires intervention include Grade 3 NCI CTC toxicity, a laboratory test twice the upper limit of normal, an abnormal finding on EEG or ECG not present at baseline. Intervention will be determined by the safety monitor and may include consultation, additional studies, or withdrawing the patient from the protocol.

The blind for an individual may need to be broken even for non-serious, expected, or unrelated AEs or as requested by local regulatory authorities or where, in the view of the safety monitor, knowledge of the identity of the study drug is essential to appropriately manage an adverse event.

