## **15. DATA AND SAFETY MONITORING**

### **15.1 Study Monitor**

This protocol will utilize a Safety Monitoring Committee (SMC) to review AEs and safety reports. The Safety Monitoring Committee will be composed of:

[name] is the Program Director of the Division of Clinical Research, NINDS. He is a board-Certified neurologist with extensive clinical trial experience. [name] is a board-certified neurologist and a member of [name] research section at NIH. She has extensive neurology experience.

The monitoring plan will include SMC review once six subjects have completed the treatment phase (Period 1 and Period 2) of the study. Thereafter, the SMC will review safety data, including seizure frequency, toxicity reports, neuropsychological and mood testing, laboratory tests, EEG, ECG and clinical examination once per year until the end of the trial.

Results will be reported to the Principal Investigator, IRB, and NINDS Clinical Director. Data review will be blinded, and no interim analysis is planned.

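### Section 8.1 gives the safety monitor the decision on events meeting its criteria, but the only stated route for a nonserious event is periodic reporting, which can be 6 to 12 months later

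*Combined protocol and SAP*

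**What the plan says.** **Who decides.** Section 8.1 sets the triggers: "Criteria to be used to decide whether a report or test result requires intervention include Grade 3 NCI CTC toxicity, a laboratory test twice". The laboratory threshold is measured against the top of the normal range, and a new EEG or ECG abnormality is the remaining trigger. The section assigns the decision: "Intervention will be determined by the safety monitor and may include consultation, additional studies, or withdrawing the patient from the protocol". Section 8 has almost the same sentence with the role spelled out: "Intervention will be determined by the independent subject safety monitor and may include consultation, additional studies, or withdrawing the patient from the protocol". The safety monitor of 8.1 is therefore read here as the independent monitor of section 8 (the ISSM), not the SMC.

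**When that person is told.** Sections 8 and 17 route by seriousness.
- Serious events: section 8 requires them to reach the ISSM "immediately, but no later than 48hrs from the time the PI learns of an event". Section 17 agrees: "The PI will immediately (no later than 48hrs) report SAEs that are at least temporally associated with the use of the study drug".
- Nonserious events: "The PI will record nonserious AEs and report them to the ISSM at the time of 1) IRB continuing review", and also at the annual SMC meeting. Section 17 repeats this rule.

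**When the SMC meets.** Section 15.1: "The monitoring plan will include SMC review once six subjects have completed the treatment phase (Period 1 and Period 2) of the study". After that it reviews once a year.

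**The concern.** The triggers in 8.1 are defined by grade, laboratory multiple or a change from baseline. The reporting routes are defined by seriousness. The two do not line up. A laboratory value at twice the limit or a new EEG abnormality can be nonserious, and so can a Grade 3 event. If the reporting rules are followed as written, such a finding waits for a periodic report before the person named to decide on it has seen it.

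At stake is a patient-level safeguard. Section 1.4 says the drug has not yet been used in children, and section 3.2 admits patients from age 4. Sections 4.4, 4.4.7 and 4.8 place the on-treatment EEG and blood tests at the end of each phase. A Phase 1 finding will therefore often surface just before washout, and the patient may enter Phase 2 before the monitor has been told.

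**Working it through.** The plan gives no figure for this delay, so there is none to reproduce. The check uses the plan's own intervals.

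**Inputs**
- Serious-event route: 48 hours (sections 8 and 17).
- Nonserious route: two kinds of occasion, IRB continuing review and the annual SMC meeting (sections 8 and 17).
- SMC interval: one year after the first review (section 15.1).
- Continuing-review interval: not defined. Yearly (52 weeks) is assumed, because section 14 refers to annual IRB review and section 17 to annual presentation to the IRB.
- Spacing between the two yearly occasions: not stated, so the full range is shown.
- Phase length: 6 months +/- 2 weeks. Washout: 9 weeks +/- 2 weeks, that is 7 to 11 weeks (section 4.1.1).

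**Longest wait.** With two yearly occasions *k* months apart (*k* from 0 to 6), the longest gap is 12 - *k* months.
- Occasions coincide (*k* = 0): 12 months.
- Three months apart: 9 months.
- Evenly staggered (*k* = 6): 6 months.

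**Before the first SMC review.** That review needs six subjects to finish both periods. One subject's two phases and washout take nominally 26 + 9 + 26 = 61 weeks, about 14 months, before titration is counted. If the annual meeting means the section 15.1 series, continuing review is the only stated occasion until then, and the longest wait is 12 months.

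**Findings from the end-of-Phase-1 tests.** Let *w* be the weeks from testing to the end of washout, and assume findings fall evenly over the reporting year. The share reported after *w* is:
- one occasion per year, or two that coincide: 1 - *w*/52;
- two evenly staggered occasions, 26 weeks apart: 1 - *w*/26.

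| *w* (weeks) | Occasions coincide | Evenly staggered |
|---|---|---|
| 7 | 1 - 7/52 = 0.87 | 1 - 7/26 = 0.73 |
| 9 | 1 - 9/52 = 0.83 | 1 - 9/26 = 0.65 |
| 11 | 1 - 11/52 = 0.79 | 1 - 11/26 = 0.58 |

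The range is about 58% to 87%. Intermediate spacings stay inside it: once the occasions are at least *w* weeks apart, the share is (52 - 2*w*)/52, the staggered value.

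**Events arising during a phase**, such as a nonserious Grade 3 toxicity reported at a fortnightly contact. If the event time is uniform over the 6 months, the mean time left in the phase is 3 months. The share reported after the phase has ended is 1 - 3/12 = 0.75 if the occasions coincide, and 1 - 3/6 = 0.50 if evenly staggered.

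**The case against.** The best reply is that patients are not left unprotected.
- Section 8 lets investigators withdraw a subject for safety, with no condition on grade, attribution or the monitor's agreement. It also removes patients whose change in status needs medical intervention, and takes off drug those who cannot tolerate it.
- Section 8 lets the investigator's own judgement start dose reduction for related Grade 3 toxicity and withdrawal of medication for related Grade 4.
- Section 4.5.3 delays or reduces dosing for side effects.
- Section 4.1.1 requires contact with families at least every two weeks.

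All of this stands. A reader might infer that nobody can act until a yearly review, and the documents do not support that. These powers still do not bring an 8.1 finding to the person assigned to decide on it. An asymptomatic laboratory or EEG finding, or a Grade 3 event not judged probably or definitely related, has no specific investigator rule beyond the general power to withdraw.

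Second, the reporting passages never say that these are the only contacts. The monitor also approves continued follow-up off drug, and section 8.1 foresees unblinding even for nonserious events. Both imply case-by-case contact. That is fair, but no route or time limit for it is written. Section 8's promise of timely feedback applies only once the reports have arrived. Section 8.1 also covers test results, whereas the periodic route is written for adverse events; a result not recorded as an adverse event has no stated route at all.

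Third, one might blame the routing for every decision that falls after a full treatment phase. For scheduled blood tests and EEG, the timing within the phase comes from the test schedule, and faster reporting would not change it.

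Fourth, one might picture a patient harmed by SGS-742 in Phase 1 going straight on to more of it. The crossover does not support that: after taper and washout, such a patient receives placebo. The examining physicians do not know the order, however, and the monitor's decision is due in either case.

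**Conclusion.** The point holds as a conflict between stated rules. Sections 8 and 8.1 assign the safety monitor decisions on findings that need not be serious, while sections 8 and 17 give fast routing only to serious ones. The stated route can bring a nonserious finding to the monitor up to about 6 to 12 months late, against 48 hours for a serious event. About 58% to 87% of end-of-Phase-1 findings would be reported after the washout.

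These figures rest on yearly continuing review, events spread evenly over the year, and no informal contact. The top of the range, 79% to 87%, applies only if there is in effect one report a year; with two evenly staggered occasions it is 58% to 73%.

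The defect is confined to the monitor's decision. It does not remove the investigators' authority to act, and it does not bear on the efficacy analysis.

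**What to change.** Reconcile section 8.1 with the reporting rules in sections 8 and 17. In both reporting passages, extend the expedited report to the safety monitor to any event or test result that meets an 8.1 criterion, whether or not it is serious. Keep periodic reporting for all other nonserious adverse events. How an open finding is handled clinically between Phase 1 and Phase 2 is for the sponsor to decide, and no rule is proposed here.

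The cost is about one sentence in each of the two passages, and a few more individual reports from 22 patients to a monitor already in place.
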